10.5 Correlative/special studies

Correlative studies are mandatory for all participants.

10.5.1 Correlation of drug response to PI3K pathway activation status

For pathway response studies we will assess activation of the PI3K pathway members in archival FFPE tissue. Previous studies and our own data have demonstrated the reliability of pathway members pAKT, pS6, and p4EBP1 in readouts of pathway modulation. The level of PI3K pathway activation will be determined by semi-quantitative immunohistochemical scoring for pAKT, pS6, and p4EBP1. All pathway modulation scores will be correlated with response to study drug. The studies will be performed in the [name] laboratory (MSKCC).

10.5.2 Characterization of mutational abnormalities

Participants tumor tissue will be assessed for mutational abnormalities, DNA will be extracted from FFPE tumor tissue. We will also collect germline DNA from whole blood collection (See 10.5.5). DNA extraction, quantification, and quality control will be performed according to established protocols in the [name] laboratory. Through target sequencing using the Miseq technology (performed at the MSKCC Geoffrey Beene Translational Oncology facility) mutational abnormalities including but not limited to CD79a, CD79b, PIK3Ca, PIK2CB, PIK3CD, MYD88, CARD11, and TNFAIP2 will be assessed and correlated with response to study drug treatment.

10.5.3 Correlation of MR spectroscopy changes to buparlisib as a potential biomarker

Research on cancer metabolism has identified a link between deregulated signaling pathways and altered cellular metabolism. These changes in cancer cell metabolism can be measured by magnetic resonance spectroscopy (MRS) and might serve as a possible biomarker of therapeutic effect. Using ¹H MRS in orthotopic glioblastoma models, Koul et al (2010) have demonstrated that inhibition of the PI3K pathway results in a decrease in total choline-containing metabolite levels, composed of choline, phosphocholine, and glycerophosphocholine. Therefore ¹H MRS could be used as a powerful tool to probe the change in cellular metabolism before and after initiation of study drug.

10.5.4 Correlation of ADC/DWI/perfusion MRI imaging to changes to buparlisib

ADC signal on MRI is inversely correlated with cell density in PCNSL. Therefore a high ADC correlates with a low cell number and was associated with better outcome (Barajas, 2009). We want to further investigate MRI changes in ADC, DWI, and perfusion imaging in response to study drug and PI3K pathway inhibition and plan to correlate MR imaging changes with clinical outcome.

10.5.5 Germline DNA collection

Whole blood will be collected on cycle 1 day 15 (+/- 4 days). Blood will be collected in an K2EDTA containing blood collection tube (lavender top tube). Blood will be stored in the [name] lab prior to DNA isolation.

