2.0 OBJECTIVES AND SCIENTIFIC AIMS

2.1 Primary Objective:

- To explore the therapeutic efficacy of buparlisib in patients with PCNSL and SCNSL as measured as progression free survival at 24 weeks (PFS24w)

2.2 Secondary Objectives:

- To explore the safety and tolerability of buparlisib in PCNSL and SCNSL patients by assessing the frequency and severity of adverse events
- To assess overall response rate (ORR) on MR imaging in patients with PCNSL and SCNSL receiving buparlisib
- To assess progression free survival at 12 weeks (PFS12w) and 48 weeks (PFS48w) in patients with PCNSL and SCNSL receiving buparlisib
- To assess the duration of response (DoR) and overall survival (OS) in patients with PCNSL and SCNSL receiving buparlisib
- To evaluate CSF pharmacokinetics of buparlisib by measuring drug concentration in serum and CSF samples

2.3 Exploratory Objectives:

- To correlate differences in drug response to PI3K pathway activation status through mutational and immunohistochemical analysis of PI3K pathway members such as but not limited to phospho-AKT, phospho-S6, phospho-4EBP1
- To characterize mutational abnormalities in paired tumor/germline DNA in PCNSL/SCNSL patients and correlated with drug response

- To correlated changes on ADC/DWI/perfusion MRI imaging to drug response
- To assess neurologic functioning using the Neurologic Assessment in Neuro-Oncology (NANO)

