6.1 Subject Inclusion Criteria

Patients eligible for inclusion in this study have to meet all the following criteria:

- Participants must be able to understand and be willing to sign a written informed consent document.
- Subjects must be at least 18 years of age on the day of consenting to the study.
- Histologically documented PCNSL or SCNSL. Patients with SCNSL need to have cytology or tissue biopsy documenting lymphomatous involvement of the CNS
- Patients must have relapsed/refractory PCNSL or relapsed/refractory SCNSL
- All patients need to have received at least one prior CNS directed therapy. There is no restriction on the number of recurrences.
- Patients with parenchymal lesions must have unequivocal evidence of disease progression on imaging (MRI of the brain or head CT) 21 days prior to study registration. For patients with leptomeningeal disease only, CSF cytology must document lymphoma cells and/or imaging findings consistent with CSF disease 21 days prior to study registration.
- Participants must have a Karnofsky performance status (KPS) of ≥ 50 .
- Participants must have adequate bone marrow and organ function shown by:

MEMORIAL SLOAN-KETTERING CANCER CENTER IRB PROTOCOL

IRB#: 14-177 A(5)

- Absolute neutrophil count (ANC) $\geq 1.5 \times 10^9/L$
- Platelets $\geq 100 \times 10^9/L$ and no platelet transfusion within the past 14 days prior to study registration
- Hemoglobin (Hgb) ≥ 9 g/dL and no red blood cell (RBC) transfusion within the past 14 days prior to study registration
- International Normalized Ratio (INR) ≤ 1.5
- Alanine aminotransferase (ALT) and aspartate aminotransferase (AST) ≤ 1.5 times the ULN.
- Serum bilirubin \leq upper limit of normal; or total bilirubin $\leq 2.0 \times$ the ULN with direct bilirubin within the normal range in patients with well documented Gilbert Syndrome.
- Participants must be able to take oral medication.
- Patients must be able to tolerate MRI scans.
- Patients must be able to tolerate lumbar puncture and/or Ommaya taps.
- Participants must have recovered to grade 1 toxicity from prior therapy.
- Participants must be able to submit 20 unstained slides from the initial tissue diagnosis for confirmation of diagnosis and correlative studies
- Life expectancy of > 3 months (in the opinion of the investigator)

Note: Prior autologous stem cell transplant as well as radiation to the CNS is **NOT** an exclusion criterion. Prior allogenic stem cell transplant **IS** an exclusion criterion.

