History, Physical and neuroexam	X	X		X		X	X	
Vital signs (blood pressure, pulse, respiration rate, temperature, height, weight) and KPS (Appendix 6)	X	X		X		X	X	
Serum pregnancy test (if applicable)	X	X		X		X		
Adverse event assessment	X			X		X	X	
Hematology group (CBC & diff)	X	X	X	X	X	X		
Chemistry group (Sodium, Potassium, Calcium, AST, ALT, Alk Phos, Total Bilirubin, Glucose, Creatinine)	X	X	X	X	X	X		
Fasting plasma glucose	X	X	X	X	X	X		
Coagulation (PT, PTT, INR)	X	X		X		X		
HbA1c	X							
8h fasting C-peptide	X							
Lipid panel	X			X*				
Amylase, lipase	X					X		
LDH	X							
Hepatitis B and C screen	X							
12-lead EKG	X			X ^s				
Chest X-ray				X ^s				
MUGA/ECHO	X							
HIV screen	X							
Bone marrow aspirate and biopsy	X							
PET brain and body	X							
PHQ-9 Patient self-rating mood scale	X		X	X	X (1)	X		
GAD7 Patient self-rating mood scale	X		X	X	X (1)	X		
NANO Score Assessment	X			X ^s		X		
Cerebrospinal fluid (CSF) Analysis including cytology	X			X(2)		X(2)		
Contrast-enhanced MRI/CT of the brain and total spine with perfusion	X			X(3)		X(3)		
Response evaluation				X (4)		X		
Computed tomography of chest, abdomen, pelvis	X							
Ophthalmologic evaluation including slit lamp exam	X							
PK BKM120 CSF			X(5)					
PK BKM120 Blood			X(6)					
Blood collection for genomic DNA			X					
Collection of archival FFPE tumor samples	X						X(7)	

- (1): PHQ-9 and GAD7 will be collected on day 15 of cycle 1 and day 1 and day 15 during cycle 2; then only on day 1 on subsequent cycles
 (2): Collection on day1 of all odd cycles starting on cycle 3; for patients with CSF disease only; response to treatment will be measured in CSF (+/- 4 days)
 (3): Imaging on day 1 of all odd cycles starting with cycle 3; MRI brain for patients with brain disease, MRI total spine for patients with intraspinal disease; MRI brain and total spine for patients with brain and spine disease as well as leptomeningeal disease (+/- 4 days)
 (4): Response will be evaluated on day 1 of all odd cycles starting with cycle 3
 (5): Patients with Ommaya reservoir: CSF collection at 1h, 2h, 4h after drug administration; no Ommaya: CSF collection through

lumbar puncture 2h after drug administration (+/- 30 min)

(6): Patients with Ommaya reservoir: Blood collect parallel to CSF collection at 1h, 2h, 4h after drug administration; no Ommaya: blood collection parallel to CSF collection through lumbar puncture 2h after drug administration (+/- 30 min)

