10.2 Pharmacokinetic analysis and evaluation of study drug penetration into the CSF space

In phase I clinical trials with buparlisib, preliminary PK data showed that buparlisib accumulated ~3 fold in achieving steady state, consistent with an effective half-life of ~ 40 hours. Steady state can be reached after approximately 7-10 days of daily dosing in most participants.

On day 15 of cycle 1, patients will undergo CSF and plasma pharmacokinetic analysis. At day 15, the study drug has reached steady state. Patients with an Ommaya reservoir will undergo taps of their reservoir at 1h, 2h and 4h after drug administration. Patients without an Ommaya reservoir will undergo a single spinal tap at 2h after study drug administration. The patient will have plasma collection in parallel (patients with Ommaya reservoir: plasma collection at 1h, 2h, and 4h post drug administration; patients without Ommaya reservoir: plasma collection at 2h post drug administration. Each draw should be collected at +/- 30 min of each time point. CSF and plasma concentrations of the drug will be measured by liquid chromatography with tandem mass spectrometry to derive a CSF/plasma concentration. Samples will be stored in the [name] laboratory and analyzed at the end of the study.

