Frequencies of toxicities will be summarized based on the Common Toxicity Criteria version 4.0. Adverse events that occur will be reported for and described in terms of incidence and severity. Objective response rate (defined as proportion of patients who achieve a complete and partial response among all patients) will be estimated along with a 95% confidence interval. For patients who respond to treatment (complete or partial response), duration of response will be calculated from the date of response to the date of progression of disease. Patients still responding at date of last follow-up will be censored. Overall survival will be calculated as the time from the start of treatment to the date of death or last follow-up. Overall survival and duration of response will be calculated using Kaplan-Meier methodology.

Pharmacokinetic parameters including half-life, C_{max} , AUC, volume of distribution, and clearance will be determined using non-compartmental methods via WinNonlin (Pharsight, Mountain View, CA). Standard descriptive statistics (mean, standard deviation, median, range) will be presented on all parameters for both serum and CSF samples.

Mutational abnormalities (mutant or not) will be assessed for the following genes: A20, CARD11, CD79B, PIK3CA, PIK3CD and MYD88. Additionally, the phosphorylation status of the following members of the PI3K pathway will be assessed through immunohistochemical staining (activated or not activated). Both, mutational abnormalities as well as immunohistochemical status will be cross tabulated with patient outcomes such as PFS24w and ORR. Associations will be assessed using Fishers exact test. For patients who receive MR spectroscopy peak values will be described and graphically presented through course of treatment. Perfusion data (ADC value categorized as high versus low) will be correlated with patient outcome if data permit.

The evaluation of NANO will be measured by the distribution of change from baseline in the level of function score for each domain.

It is anticipated that 1-2 patients per month will be accrued to this study and the study will be completed within 2 years. Accrual is limited to 10 patients with SCNSL and 11 patients with PCNSL.

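### Germline blood is scheduled only at cycle 1 day 15, so patients lost before about day 11 lack the germline half of the exploratory paired analysis

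*Combined protocol and SAP*

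**What the plan says.** Section 10.5.5 schedules the germline sample once: "Whole blood will be collected on cycle 1 day 15 (+/- 4 days". The Table 6 row "Blood collection for genomic DNA" carries one mark, in the same column position as the two PK rows. Section 10.2 fixes that column: "On day 15 of cycle 1, patients will undergo CSF and plasma pharmacokinetic analysis". The row has no mark at screening, cycle 1 day 1, later cycles, end of treatment or the 30-day visit, and no replacement sample is described.

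Section 10.5.2 takes mutations from the archival tumour DNA and points to the same blood for the germline part: "We will also collect germline DNA from whole blood collection (See 10.5.5". No other germline source is named.

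The exploratory objective in section 2.3 is "To characterize mutational abnormalities in paired tumor/germline DNA in PCNSL/SCNSL patients and correlated with drug response". The tumour half of each pair is secured at entry, because section 6.1 states "Participants must be able to submit 20 unstained slides from the initial tissue diagnosis for confirmation of diagnosis and correlative studies".

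Section 14.0 plans the outcome analysis. Mutation status, as a yes/no variable, and "immunohistochemical status will be cross tabulated with patient outcomes such as PFS24w and ORR". It continues: "Associations will be assessed using Fishers exact test". It does not say what happens to a patient without germline DNA.

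**The concern.** Day 15 has a reason for PK: section 10.2 wants steady state. No such reason applies to germline sequence, which treatment does not alter. The effect of tying the tube to the PK visit is that only the germline half of the pair depends on the patient still being on study at about day 11 to 19.

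Those who are gone by then are mostly early failures. Section 12.2 counts clear clinical worsening, or failure to return because of death or deterioration, as progression, so a patient can fail well before the first scan. The missing germline samples would then be concentrated at one end of the outcome that objective 2.3 wants to correlate with genotype, in a trial of only 21 patients. After an early death the sample cannot be recovered.

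**Working it through.** **1. The plan's own figure.** The documents give no number for the germline or mutation analysis. The nearest figure is the exact interval in Table 14 for 12 of 21, which reproduces as 34.02% to 78.18%. It uses all 21 patients and does not depend on this sample.

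**2. Who misses the draw.** The window is day 15 - 4 = day 11 to day 15 + 4 = day 19. A patient who leaves before day 11 misses it on schedule. One who leaves between day 11 and day 19 may or may not be sampled. A temporary dose hold does not lose the sample, because section 9.1 keeps evaluations running during holds.

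**3. How many.** Inputs: N = 21 (section 14.0). Median PFS is an assumption, set at 2 to 5.7 months, the span of the short-PFS chemotherapy rows of Table 1. PFS is assumed exponential, with 30.4375 days per month.

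Formula: p(d) = 1 - exp(-ln 2 × d / (median × 30.4375)); expected number = 21 × p(d).

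Example, median 2 months and d = 11: ln 2 × 11 / 60.875 = 0.125, so p = 11.8% and 21 × 0.118 = 2.5.

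| Assumed median (months) | p by day 11 | Expected of 21, day 11 | day 15 | day 19 |
|---|---|---|---|---|
| 2 | 11.8% | 2.5 | 3.3 | 4.1 |
| 2.8 | 8.6% | 1.8 | 2.4 | 3.0 |
| 4.5 | 5.4% | 1.1 | 1.5 | 1.9 |
| 5.7 | 4.3% | 0.9 | 1.2 | 1.5 |

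Day 11 is the column that matters for a certain miss: 0.9 to 2.5 of 21. The highest median in Table 1 is 26 months. There the exponent is ln 2 × 11 / (26 × 30.4375) = 0.0096, giving p = 0.96% and about 0.2 patients.

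**4. Effect on success rates in the paired set.** If k early failures are missing, the rate becomes successes / (21 - k).
- With 8 successes: 38.1% (k = 0), 40.0% (k = 1), 42.1% (k = 2).
- With 12 successes: 57.1%, 60.0%, 63.2%.

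**5. Effect on the association.** Let the share of failures that keep a germline sample be r_m among mutants and r_w among wild type. Then the observed odds ratio = true odds ratio × r_w / r_m. If r_m = r_w, meaning that loss depends on failure alone, the odds ratio is not shifted systematically and only precision suffers. It shifts when failures in one genotype occur earlier than in the other.

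Invented table for illustration: mutant 7 successes and 3 failures, wild type 2 and 9. Fisher's exact test:
- All 21 patients: OR 10.5, p = 0.030.
- One wild-type early failure missing: 10.5 × 8/9 = 9.33, p = 0.07.
- Two wild-type early failures missing: 10.5 × 7/9 = 8.17, p = 0.07.
- One mutant and two wild-type failures missing: 10.5 × (7/9)/(2/3) = 12.25, p = 0.057.

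The shift can go either way, and one lost pair can change the reading of a table this small.

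**The case against.** The strongest reply is that nothing in the plan removes these patients from the test it specifies. Section 14.0 cross-tabulates mutation status with outcome and does not mention germline DNA. Section 10.5.2 calls mutations from tumour tissue, which section 6.1 requires of everyone. The requirement for pairs appears in objective 2.3. This stands. A reader might infer that early failures drop out of the mutation-response analysis altogether, and the documents do not support that. What is shown is a missing comparator for the paired objective. Equally, the plan nowhere says that tumour-only calls will be used.

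The count is also open to challenge, and most of that challenge stands. Using day 15 and the shortest medians, one might infer 2 to 3 lost patients, but the window opens at day 11. The first scheduled imaging is cycle 3 day 1, which is day 57 (2 × 28 + 1), so before day 11 a failure would normally be recorded only through death or clear clinical worsening. Entry requires a judged life expectancy above 3 months and KPS of at least 50. A constant hazard from day 0 therefore probably overstates early events. On the other side, early withdrawals and toxicity removals lose the sample too and are not counted in the calculation.

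Two further inferences go too far. Not everyone lost early is a PFS24w failure: under section 12.8 a patient who stops for toxicity or by choice and is still followed is not an event, although section 14.0 does count loss to follow-up as one. Nor is it certain that such patients can never be sampled: Table 6 has blood tests at end of treatment, section 13.0 has a 30-day visit, and an unscheduled draw is not forbidden. None is scheduled for germline DNA, however.

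The shared visit with PK may be a matter of logistics. No reason is stated, and blood is already scheduled on day 1.

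**Conclusion.** The point holds as a minor one (worth considering). The only scheduled germline draw comes two weeks after treatment starts, without a stated or evident benefit, and patients gone before about day 11 are not scheduled to supply the germline half of the pair. Under the exponential assumption with medians of 2 to 5.7 months, that is roughly 1 to 2 of 21, and probably fewer in the population that section 6.1 selects.

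In the paired set the loss raises apparent success rates by about 2 to 6 percentage points in the examples above and costs precision. A reader might infer that loss related to outcome biases the association by itself. It does not: bias in the odds ratio also requires genotype to be related to very early failure. That possibility cannot be set aside, since the link between genotype and outcome is what the objective examines.

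Only the exploratory objective is touched. PFS24w in all 21 patients and the rule of at least 12 of 21 are unaffected, and neither safety nor the overall ORR uses this sample.

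**What to change.** In section 10.5.5 and the genomic DNA row of Table 6, move the germline tube to cycle 1 day 1 before the first dose, taken with the hematology and chemistry blood already scheduled there. Allow a later draw only if that one was missed.

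This brings the loss due to timing to 0 of 21 treated patients, provided the day 1 draw is made. The cost is two wording changes and one tube moved to an existing draw, with no added visit or needle stick. The small downside is storing samples from a few patients who leave very early.

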11.0 TOXICITIES/SIDE EFFECTS

11.1. Anticipated toxicities

In order for an event to be expected (known correlation to the study drug) for the purposes of adverse event reporting, the event must be included in this section.

A list of adverse events of all grades suspected to be buparlisib treatment related in phase I studies, organized by CTCAE v4.0 category includes:

- Cardiovascular: Hypertension
- Gastrointestinal: Diarrhea, dyspepsia, mucosal inflammation, nausea
- General disorders: Asthenia, fatigue, pyrexia
- Investigations: Aminotransferase elevation/transaminitis, GGT elevation, hyperbilirubinemia, lymphopenia, elevated lipase
- Metabolism and nutritional disorders: Hyperglycemia, hypophosphatemia, anorexia
- Nervous system disorders: Dizziness
- Psychiatric disorders: Mood alterations including depression and anxiety
- Pulmonary: Pneumonitis
- Skin: Rash, pruritis.

The safety experience for single agent buparlisib in trial CBKM120X2101 is summarized in Table 10

Table 10: Most frequent Adverse Event (≥15%) related to study drug in study CBKM120X2101 (n=81)

Event	All grades	Grade 3/4
Fatigue/asthenia	31 (38.3%)	3 (3.7%)
Decreased appetite	24 (29.6%)	-
Diarrhea	24 (29.6%)	3 (3.7%)
Hyperglycemia	24 (29.6%)	4 (4.9%)
Nausea	24 (29.6%)	-
Rash	22 (27.2%)	4 (4.9%)
Mood altered/emotional disorder/affective disorder	17 (21%)	4 (4.9%)
Transaminases increased	16 (19.8)	9 (11.1%)
Anxiety	14 (17.3%)	1 (1.2%)
Depression	14 (17.3%)	1 (1.2%)

11.2 Toxicity Management

Routine supportive care is recommended. Routine prophylactic use of G-CSF is not permitted. Please refer to Table 11 for toxicity specific modifications.

Table 11: Criteria for interruption and re-initiation of buparlisib treatment

Worst toxicity (CTCAE 4.03 Grade)**	Dose Modifications for Buparlisib
HEMATOLOGICAL	
Neutropenia (ANC)	
Grade 1 (ANC < LLN - $1.5 \times 10^9/L$) Grade 2 (ANC < $1.5 - 1.0 \times 10^9/L$)	Maintain dose level
Grade 3 (ANC < $1.0 - 0.5 \times 10^9/L$) Grade 4 (ANC < $0.5 \times 10^9/L$)	Omit dose until resolved to \leq Grade 1, then: If resolved in ≤ 7 days, then maintain dose level If resolved in > 7 days, then $\downarrow 1$ dose level
Febrile neutropenia (ANC < $1.0 \times 10^9/L$, with a single temperature of ≥ 38.3 °C or a sustained temperature of ≥ 38 °C for more than one hour)	Omit dose until resolved, then $\downarrow 1$ dose level
Thrombocytopenia	
Grade 1 (PLT < LLN - $75 \times 10^9/L$) Grade 2 (PLT < $75 - 50 \times 10^9/L$)	Maintain dose level
Grade 3 (PLT < $50-25 \times 10^9/L$)	Omit dose until resolved to \leq Grade 1, then: If resolved in ≤ 7 days, then maintain dose level If resolved in > 7 days, then $\downarrow 1$ dose level
Grade 4 (PLT < $25 \times 10^9/L$)	Omit dose until resolved to \leq Grade 1, then $\downarrow 1$ dose level
RENAL	
Serum creatinine	
Grade 1 (< 2 x ULN)	Maintain dose level
Grade 2 (2 – 3 x ULN)	Omit dose until resolved to \leq grade 1, then: If resolved in ≤ 7 days, then maintain dose level If resolved in > 7 days, then $\downarrow 1$ dose level
Grade 3 (> 3.0 – 6.0 x ULN)	Permanently discontinue patient from buparlisib
Grade 4 (> 6.0 x ULN)	Permanently discontinue patient from buparlisib
HEPATIC	
Bilirubin (*for patients with Gilbert Syndrome these dose modifications apply to changes in direct bilirubin only) will be fractionated if elevated	
Grade 1 (> ULN - $1.5 \times ULN$)	Maintain dose level with LFTs* monitored as per protocol
Grade 2 (> $1.5 - 3.0 \times ULN$) with ALT or AST $\leq 3.0 \times ULN$	Omit dose until resolved to \leq Grade 1, then: If resolved in ≤ 7 days, then maintain dose level If resolved in > 7 days, then $\downarrow 1$ dose level
Grade 3 (> $3.0 - 10.0 \times ULN$) with ALT or AST $\leq 3.0 \times ULN$	Omit dose until resolved to \leq Grade 1, then: If resolved in ≤ 7 days, $\downarrow 1$ dose level If resolved in > 7 days discontinue patient from buparlisib
Grade 4 (> $10.0 \times ULN$)	Permanently discontinue patient from buparlisib
AST or ALT	
Grade 1 (> ULN – $3.0 \times ULN$)	Maintain dose level with LFTs* monitored per protocol

MEMORIAL SLOAN-KETTERING CANCER CENTER
IRB PROTOCOL

IRB#: 14-177 A(5)

Grade 2 (> 3.0 - 5.0 x ULN) without total bilirubin elevation to > 2.0 x ULN	Can continue treatment at ↓ 1 dose level
Grade 3 (> 5.0 - 20.0 x ULN) without total bilirubin elevation to > 2.0 x ULN	Omit dose until resolved to ≤ Grade 1, then ↓ 1 dose level** If no recovery in ≤28 days, discontinue buparlisib permanently
Grade 4 (> 20.0 x ULN) without bilirubin elevation to > 2.0 x ULN	Discontinue buparlisib permanently
AST or ALT and concurrent Bilirubin	
AST or ALT > 3.0 x ULN and total bilirubin > 2.0 x ULN	Permanently discontinue buparlisib***

*(LFTs include albumin, ALT, AST, total bilirubin (fractionated if total bilirubin > 2.0 x ULN), alkaline phosphatase (fractionated if alkaline phosphatase is grade 2 or higher) and GGT)
 
**In case of recurring Grade 3 or higher toxicity after re-challenge, patient should be permanently discontinued
 
***All patients with ALT or AST>3.0x ULN and total bilirubin >2.0x ULN in the absence of cholestasis must immediately be withdrawn from buparlisib and every attempt should be made to carry out the liver event follow-up assessments as described below in section 11.11.1.2: Management of Hepatotoxicity (ALT and/or AST> 3.0x ULN and total bilirubin >2.0x ULN) in patients receiving buparlisib and Viral Serology and other tests for hepatotoxicity follow-up.
 
Hepatic toxicity monitoring (*for patients with Gilbert Syndrome: total and direct bilirubin must be monitored, intensified monitoring applies to changes in direct bilirubin only; the monitoring includes the following LFTs: albumin, ALT, AST, total bilirubin (fractionated if total bilirubin > 2.0 x ULN), alkaline phosphatase (fractionated if alkaline phosphatase is grade 2 or higher) and GGT):
 
Cycle 1 and 2: every other week (if visit schedule allows a more frequent monitoring this should be considered) or more frequently if clinically indicated especially for patients with borderline acceptable AST/ALT, or bilirubin* values
 
Cycle 3 and onward: monthly or more frequently if clinically indicated
 
In case of any occurrence of ALT/AST, or bilirubin* increase ≥ grade 2 the liver function tests must be monitored weekly or more frequently if clinically indicated until resolved to ≤ grade 1
 
In case of any occurrence of ALT/AST, or bilirubin* increase ≥ grade 3 the liver function tests must be monitored weekly or more frequently if clinically indicated until resolved to ≤ grade 1; hereafter the monitoring should be continued every other week or more frequently if clinically indicated until the end of treatment with study medication
 
Patients who discontinued study treatment should be monitored weekly, including LFTs* or more frequently if clinically indicated until resolved to ≤ grade 1 or stabilization (no CTCAE grade change over 4 weeks).
	
ENDOCRINE/METABOLIC	
Fasting Plasma Glucose (FPG)	
Grade 1 (> ULN - 160 mg/dL) (> ULN - 8.9 mmol/L)	Maintain dose level, check FPG every week 
 ● initiate or intensify medication with appropriate anti-diabetic treatment as per investigator's discretion ● instruct patient to follow dietary guidelines according to local and/or institutional standards for management of diabetes mellitus (such as those provided by the American Diabetes Association) during the study ● consider use of oral anti-hyperglycemic therapy such as metformin (or intensify existing medications), ● check FPG at least weekly for 8 weeks, then continue checking at least every 2 weeks
Grade 2 (>160 - 250 mg/dL) (> 8.9 - 13.9 mmol/L)	
 ● If signs or symptoms of hyperglycemia (for example, mental status changes, excessive thirst, polyuria), manage as for Grade 3 hyperglycemia (see below) ● If asymptomatic, maintain dose and re-check FPG

MEMORIAL SLOAN-KETTERING CANCER CENTER
IRB PROTOCOL

IRB#: 14-177 A(5)

	
within 24 hours. If grade worsens or improves then follow specific grade recommendations. If FPG remains at Grade 2:
 
 ○ maintain dose level and monitor FPG at least weekly until FPG resolves to \leq Grade 1 ○ initiate or intensify medication with appropriate anti-diabetic treatment such as metformin; consider adding a second oral agent if not improvement after several days. ○ instruct patient to follow dietary guidelines according to local and/or institutional standards for management of diabetes mellitus (such as those provided by the American Diabetes Association) during the study ○ if FPG does not resolve to \leq Grade 1 within 14 days after institution of appropriate anti-diabetic treatment reduce buparlisib by 1 dose level ● Continue with anti-diabetic treatment and check FPG at least weekly for 8 weeks, then continue checking at least every 2 weeks

Grade 3 (> 250 - 500 mg/dL) (> 13.9 - 27.8 mmol/L)
	
Omit buparlisib, initiate or intensify medication with appropriate anti-diabetic treatment, re-check FPG within 24 hours. If grade worsens or improves then follow specific grade recommendations. If FPG remains at Grade 3:
 
 ● administer intravenous hydration and intervention for electrolyte/ketoacidosis/hyperosmolar disturbances as clinically appropriate ● continue to omit buparlisib ● monitor FPG at least twice weekly until FPG resolves to \leq Grade 1 ● If FPG resolves to \leq Grade 1 in 7 days or less, then re-start buparlisib and \downarrow 1 dose level ● If FPG remains greater than Grade 1 severity for more than 7 days, then discontinue patient from buparlisib ● initiate or continue anti-diabetic treatment as appropriate 
 ○ instruct patient to follow dietary guidelines according to local and/or institutional standards for management of diabetes mellitus (such as those provided by the American Diabetes Association) during the study ○ consider use of oral anti-hyperglycemic therapy such as metformin ● check FPG at least weekly for 8 weeks, then continue checking at least every 2 weeks 
For non-fasting plasma glucose >250-500 mg/dL (> 13.9 - 27.8 mmol/L) accompanied by signs/symptoms of hyperglycemia (for example, mental status changes, excessive thirst, polyuria), or presence of blood or urine ketones, omit buparlisib and following guidance for management of Grade 3 fasting plasma glucose (FPG)

Grade 4 (> 500 mg/dL) (\geq 27.8 mmol/L)
	
Immediately omit buparlisib, initiate or intensify medication with appropriate anti-diabetic treatment, re-check within 24 hours. If grade improves then follow specific grade recommendations. If FPG is confirmed at Grade 4:
 
 ● administer intravenous hydration and intervention for electrolyte/ketoacidosis/hyperosmolar disturbances as clinically appropriate ● discontinue patient from buparlisib

MEMORIAL SLOAN-KETTERING CANCER CENTER
IRB PROTOCOL

IRB#: 14-177 A(5)

	
 ● instruct patient to follow dietary guidelines according to local and/or institutional standards for management of diabetes mellitus (such as those provided by the American Diabetes Association) during the study ● consider use of oral anti-hyperglycemic therapy such as metformin ● check FPG at least weekly for 8 weeks, then continue checking at least every 2 weeks if clinically indicated 
For non-fasting plasma glucose >500 mg/dL (> 27.8 mmol/L) accompanied by signs/symptoms of hyperglycemia (for example, mental status changes, excessive thirst, polyuria), or presence of blood or urine ketones, discontinue buparlisib and following guidance for management of Grade 4 fasting plasma glucose (FPG).

CARDIAC	
Cardiac - Left Ventricular systolic dysfunction	
Asymptomatic, resting ejection fraction 40-50%; or 10-20% drop from baseline	Maintain dose level, and continue buparlisib with caution Repeat LVEF within 4 weeks or as clinically appropriate
Symptomatic, responsive to intervention, ejection fraction 20-39% or > 20% drop from baseline	
 ● Omit buparlisib until resolved* (as defined below), then ↓ 1 dose level ● LVEF measurement to be repeated, if not resolved* within 21 days, permanently discontinue patient from buparlisib treatment
Refractory or poorly controlled, ejection fraction < 20%	● Permanently discontinue patient from buparlisib
*the event is considered resolved when the patient is asymptomatic, has a resting ejection fraction ≥ 40% and ≤20% decrease from baseline.	
Cardiac – QTc prolongation	
QTcF > 500 ms (≥ Grade 3) or > 60 ms change from baseline on at least two separate ECGs	
First Occurrence:
 
 ● omit buparlisib ● Perform an analysis of serum potassium and magnesium, and if below lower limit of normal, correct with supplements to within normal limits. Concomitant medication usage must be reviewed. ● Perform a repeat ECG within one hour of the first QTcF of > 500 ms or >60ms from baseline ● If QTcF remains > 500 ms or >60ms from baseline, repeat ECG as clinically indicated, but at least once a day until the QTcF returns to < 480 ms. Seek cardiologist input. ● Once QTcF prolongation has resolved, buparlisib may be restarted at a one lower dose level 
Second Occurrence:
 
 ● Permanently discontinue patient from buparlisib
Other Cardiac Events	
Grade 1 or 2	Maintain dose level
Grade 3	Omit dose until resolved to ≤ Grade 1, then ↓ 1 dose level
Grade 4	Permanently discontinue patient from buparlisib
OTHER	
Mood alteration/Psychiatric Disorders	
* Note: For all grades, if question 9 on the PHQ-9 has a positive response (as indicated by selecting "1",	

MEMORIAL SLOAN-KETTERING CANCER CENTER
IRB PROTOCOL

IRB#: 14-177 A(5)

"2", or "3"), omit study drug and refer patient for psychiatric consult regardless of the total questionnaire score or CTCAE grading to confirm if study drug should be interrupted or permanently discontinued.	
Grade 1*	
 ● Maintain dose level ● Consider psychiatric consultation at the investigator's discretion and introduce optimal management (e.g. as per local guidelines and/or psychiatric/expert consultation)
Grade 2*	
 ● Omit dose until resolved to \leq Grade 1 or baseline status ● Consider psychiatric consultation at the investigator's discretion and introduce optimal management (e.g. as per local guidelines and/or psychiatric/expert consultation) ● First event: if the condition resolved to Grade \leq 1 or to baseline status, continue to co-medicate and then maintain the dose level ● Second and further events: if the condition resolved to Grade \leq 1 or to baseline status, continue to co-medicate and then \downarrow 1 dose level
Grade 3*	
Omit dose until resolved to \leq Grade 1 or baseline status
 
 ● Psychiatric consultation is required and introduce optimal management ● if the condition resolved to Grade \leq 1 or to baseline status, continue to co-medicate and then \downarrow 1 dose level
Grade 4*	
Permanently discontinue patient from buparlisib
 
 ● Psychiatric consultation is required ● Introduce optimal management (e.g. as per local guidelines)
Rash	
Grade 1	Maintain dose level. Consider to initiate appropriate skin toxicity therapy (such as antihistamines, topical corticosteroids)
Grade 2	
First occurrence: Omit dose until resolved to grade \leq 1 then:
 
 ● If resolved in \leq 2 weeks, maintain dose level. ● If resolved in more than 2 weeks, \downarrow 1 dose level. 
Second occurrence: \downarrow 1 dose level. Initiate/intensify appropriate skin toxicity therapy (such as antihistamines, topical corticosteroids)

Grade 3	
First occurrence: omit dose until resolved to CTCAE Grade \leq 1; then \downarrow 1 dose level.
 
Second occurrence: permanently discontinue patient from buparlisib.
 
Consider referral to dermatologist and manage rash per dermatologist's recommendation.
 
According to the investigators discretion, a paired skin biopsy could be obtained (from both an affected and an unaffected skin area for local histopathology assessment) if clinical appropriate.

Grade 4	
Permanently discontinue patient from buparlisib.
 
Consider referral to dermatologist and manage rash per dermatologist's recommendation.
 
According to the investigators discretion, a paired skin

MEMORIAL SLOAN-KETTERING CANCER CENTER
IRB PROTOCOL

IRB#: 14-177 A(5)

	biopsy could be obtained (from both an affected and an unaffected skin area for local histopathology assessment) if clinical appropriate.
Fatigue (asthenia)	
Grade 1 or 2	Maintain dose level
Grade 3	Omit dose until resolved to \leq Grade 1, then: ● If resolved in \leq 7 days, maintain dose level ● If resolved in $>$ 7 days, \downarrow 1 dose level
Pneumonitis	please see section for additional follow up for selected toxicities
Other non- hematological adverse events	
Grade 1 or 2	Maintain dose level
Grade 3	Omit dose until resolved to \leq Grade 1, then \downarrow 1 dose level
Grade 4	Permanently discontinue patient from buparlisib Note: Omit dose for \geq Grade 3 vomiting or Grade 3 nausea only if the vomiting or nausea cannot be controlled with optimal antiemetic
Stomatitis/Oral mucositis	
Grade 1 / Tolerable Grade 2	Maintain dose level. Non-alcoholic or salt water mouth wash (see also section for additional follow up for selected toxicities)
Intolerable Grade 2 or Grade 3	First occurrence: hold until resolved to grade \leq G1 and \downarrow 1 dose level (if stomatitis is readily manageable with optimal management, re-introduction at the same level might be considered at the discretion of the investigator). Second occurrence: hold until resolved to grade \leq G1 and \downarrow 1 dose level.
Grade 4	Permanently discontinue patient from buparlisib.
** Common Terminology Criteria for Adverse Events (CTCAE) version 4.03.	

